## **1.0 Study Summary**

**Title:** Endotracheal Tube Securement Study: The Effect of Adhesive Tape Versus Endotracheal Tube Fastener on Lip Integrity, Tube Dislodgement, and Ventilator Associated Pneumonia in Critically Ill Adults

- A single center randomized controlled trial of endotracheal tube securement with adhesive tape versus endotracheal tube fastener in the incidence of lip ulcers, tube dislodgement, and ventilator associated pneumonia.

**Study Site:** Vanderbilt University Medical Center Nashville, TN

**Background:** During endotracheal intubation there are many potential complications including laryngeal trauma, bronchospasm, hypotension, airway perforation, and vertebral column injury. Following intubation for mechanical ventilation, there are several techniques to secure the endotracheal tube. The optimal stabilization method in reducing complications is unknown. We propose a randomized controlled trial to compare the effect of adhesive tape versus endotracheal tube fastener on complications including lip ulcers, endotracheal tube dislodgement, and ventilator associated pneumonia among critically ill adults requiring intubation and mechanical ventilation.

### **Primary Aim:**

- To compare the effect of adhesive tape versus endotracheal tube fasteners on the incidence of lip ulcers, tube dislodgement, and ventilator associated pneumonia among critically ill adults undergoing endotracheal intubation

### **Primary Hypothesis:**

- The use of an endotracheal tube fastener will reduce the incidence of lip ulcers, tube dislodgement, and ventilator associated pneumonia among critically ill adults undergoing endotracheal intubation

### **Inclusion Criteria:**

1. Patient is admitted to an ICU at Vanderbilt University Medical Center
2. Patient requires intubation and mechanical ventilation
3. Intubated for less than 12 hours before enrollment in the study
4. Patient anticipated to be intubated 24 hours or longer
5. Age > 18 years

### **Exclusion Criteria:**

1. Presence of oral mucosa or facial skin breakdown before study enrollment
2. Nasotracheal intubation
3. Patients with documented allergy to tape
4. Patient has facial anatomy which prevents the use of endotracheal tube fastener

5. Prisoners
6. Pregnant patients

**Consent:** Given that both techniques for securing endotracheal tubes are used in practice, appear to be arbitrarily chosen by the RT or medical team, and that there is a lack of established risk or benefit between the two techniques, this trial poses no increased risk beyond usual ICU care to the patients. Also, over 90% of patients undergoing endotracheal intubation in the ICU cannot consent for the procedure itself and choosing a securement strategy is time-sensitive as endotracheal tube securement must occur at the time of intubation, therefore it is impractical to obtain informed consent for research prior to the procedure. Given the minimal risk interventions and impracticability of informed consent, a waiver of informed consent will be requested.

**Randomization:** Using opaque envelopes available in the patient care area participating in the study, participants will be randomized 1:1 to adhesive or endotracheal tube fastener

Study Interventions:

- Endotracheal tube securement
  - Adhesive Tape: (1) Use skin preparation pad (tincture benzocaine) to prepare area over cheeks and upper lip where adhesive tape will be secured (2) Use tape to tape approach to decrease adhesiveness of tape to back of neck / hair area. (3) Secure tape around patient's neck. (4) Encircle the adhesive tape around the tube and fix to the maxilla about the upper lip and down the lower lip.
  - Endotracheal tube fastener: (1) Place upper lip stabilizer so it rests on skin between nose and lip; place skin barrier pads on cheeks. (2) Secure ETT wrap with non-slip grippers and one-click security clamp. (3) Position gliding tube shuttle; reposition as needed for oral care and pressure relief.
  - Repositioning: Frequency of repositioning of endotracheal tube in both groups will be left to the applicable ICU protocol (or discretion of the provider if no applicable protocol) and will be documented accordingly.

**Primary Endpoint** (All endpoints are collected non-invasively and are already a part of clinical data obtained in usual ICU care at the bedside or in the medical record):

- Composite of any of: presence of lip ulcer, endotracheal tube dislodgement, or facial skin tears from the time of randomization to the earlier of death or 48 hours after extubation

Secondary Endpoints:

- Presence of Lip Ulcer
- Endotracheal tube dislodgement
- Ventilator associated pneumonia incidence

- Facial skin tears
- Ventilator-free days

## **2.0 Background**

### **2.1 Complications of endotracheal tube securement**

Effective endotracheal tube securement is imperative in providing safe mechanical ventilation. Various techniques have been utilized to ensure endotracheal tube stabilization in order to maintain a patent airway and prevent complications. One common complication of endotracheal tube securement is lip ulcers. The development of lip ulcers is not rare and is associated with increased financial burden and potentially increased length of stay. Endotracheal tube dislodgement is another common complication of tube securement. It is imperative for the tube to be correctly positioned to maintain optimum airway passage and promote effective mechanical ventilation. If the tube is not secured correctly, it can become dislodged which may result in unplanned extubation, bronchospasm, and tracheal injury. Additionally, endotracheal intubation and mechanical ventilation is associated with ventilator associated pneumonia. Proper oral hygiene is essential in decreasing the incidence of ventilator associated pneumonia. Utilizing an endotracheal tube securement technique that enables providers to perform oral hygiene is imperative. It is thought that modifying endotracheal tube securement technique could reduce these complications.

## **3.0 Rationale, Aims, and Hypotheses**

In order to determine the effect of adhesive versus endotracheal tube fasteners on prevalence of lip ulcers, endotracheal tube dislodgement, and ventilator associated pneumonia among intubated critically ill patients, a randomized trial is needed.

### **Study Aims:**

#### **Primary:**

- To compare the effect of adhesive tape versus endotracheal tube fasteners on adverse effects (lip ulcers, endotracheal tube dislodgement, or facial skin tears) among critically ill adults undergoing endotracheal intubation

#### **Secondary:**

- To compare the effect of adhesive tape versus endotracheal tube fasteners on ventilator-free days among critically ill adults undergoing endotracheal intubation

### **Study Hypotheses:**

#### **Primary:**

- The use of an endotracheal tube fastener will reduce the incidence of any of lip ulcers, endotracheal tube dislodgement, or facial skin tears among critically ill adults undergoing endotracheal intubation

**Secondary:**

- The use of endotracheal tube fastener will reduce the incidence of endotracheal tube dislodgement, ventilator associated pneumonia, and facial skin tears among critically ill adults undergoing endotracheal intubation
- The use of endotracheal tube fastener will increase the number of ventilator-free days among critically ill adults undergoing endotracheal intubation

#### **4.0 Study Description**

In order to address the aims outlined above, we propose a randomized trial evaluating the impact of adhesive tape versus endotracheal tube fastener on the incidence of lip ulcers, endotracheal tube dislodgement, ventilator associated pneumonia, and facial skin tears among critically ill adults undergoing endotracheal intubation. Patients admitted to the study ICU who are deemed by their clinical team to require intubation and fulfill inclusion criteria without meeting exclusion criteria will be enrolled and randomly assigned to adhesive tape versus endotracheal tube fastener. If patients were intubated prior to admission to the intensive care unit and the intubation time was less than 12 hours from the time of admission, they will be included in the study. Data will be collected at the time of intubation and prospectively from the medical record in order to determine the effect of the assigned intervention on short- and long-term outcomes. All data are collected non-invasively and are already a part of clinical data obtained in usual ICU care at the bedside or in the medical record. No additional data will be collected that are not observed at the bedside or obtained from the medical record.

#### **5.0 Inclusion and Exclusion Criteria**

##### **5.1 Inclusion Criteria**

We will include endotracheal tube securement events in which:

1. Patient is admitted to the intensive care unit at Vanderbilt University Medical Center.
2. Planned procedure is endotracheal intubation and mechanical ventilation OR
3. Patient is intubated prior to arrival, however the intubation occurred less than 12 hours prior to admission to the intensive care unit
4. Patient is likely to be intubated > 24 hours.
5. Age > 18 years old

##### **5.2 Exclusion Criteria**

We will exclude airway management events in which:

1. Patient has presence of oral mucosa or facial skin breakdown before study enrollment

2. Patient will require nasotracheal intubation
3. Patients with documented allergy to tape
4. Patient who have facial anatomy which prevent the use of endotracheal tube fastener
5. Prisoners
6. Pregnant patients
7. Patient who the team feels must have either adhesive tape or endotracheal tube skin fasteners as the securement device

## **6.0 Enrollment/Randomization**

**6.1 Study Sites:** ICU at Vanderbilt University Medical Center

**6.2 Study Population:** The study population will be all critically ill adults admitted to an ICU service for whom the clinical team has decided to perform endotracheal intubation or for whom endotracheal intubation has been performed within 12 hours prior to admission. Patients will be excluded if they were intubated greater than 12 hours prior to admission, if they have oral mucosa or facial skin breakdown before enrollment, if they require nasotracheal intubation, or have a documented allergy to tape.

**6.3 Enrollment:** All patients will be enrolled at the time the clinical team decides that intubation is required and the patient meets inclusion but no exclusion criteria. If the patient arrives in the MICU already intubated, but has been intubated less than 12 hours and does not have exclusion criteria, they will be eligible for randomization as soon as possible (but must occur within 12 hours of the intubation) when their endotracheal tube is undergoing securement.

**6.4 Consent:** Because the intervention studied (1) is FDA approved and used according to its FDA approval as a part of routine care, (2) is an intervention the patients would arbitrarily be exposed to even if not participating in the study, and (3) is an equivalent option from the perspective of the clinical provider (otherwise patient is excluded), we feel the waiver of consent involves no more than minimal risk. Additionally, obtaining informed consent in the study would be impractical. Endotracheal intubation of acutely ill patients is frequently a time-sensitive procedure. Despite the availability of a formal informed consent document for the procedure itself, time allows discussion of risks and benefits in less than 10% of airway management events in the ICU. Because the study interventions represent minimal risk, would not adversely affect the welfare or privacy rights of the participant, and consent would be impracticable, we will request a waiver of informed consent. Information regarding the study will be available for patients and families.

**6.5 Randomization:** Computerized randomization using permuted blocks of two, four, or six will be conducted in order to generate a series of study assignments deliberately exceeding the planned enrollment number. Study assignments will be placed in opaque randomization envelopes and will be available to operators in the ICU at VUMC. Study group assignment will remain concealed to study personnel and

operators until after the decision has been made to enroll the patient in the study. Once it has been determined by the treating team that intubation is required, (or maintenance of endotracheal tube securement in patients intubated less than 12 hours prior to admission) the operator will open the envelope and follow the assignment of either adhesive tape or endotracheal tube fastener.

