## **8.0 Data Collection**

All data will be collected non-invasively and will already be a part of clinical data obtained in usual ICU care at the bedside or in the medical record. No additional data will be obtained beyond that which is obtained by bedside observation and from the electronic medical record.

**Baseline:** Age, gender, height, weight, race, active medical problems at the time of intubation, active comorbidities complicating intubation, indication for intubation, whether it is a reintubation, whether the face was soiled during the intubation

**Periprocedural:** Depth of tube as measured at lip line and position in mouth (ie 22 cm at the lip, midline) at time of securement

**In-Hospital Outcomes:** days on mechanical ventilator, ICU mortality, mortality for ventilator free days, oral mucosa assessment, facial skin integrity assessment, frequency of endotracheal tube repositioning, endotracheal tube dislodgements – defined as either complete

Principal Investigator: [name], ACNP-BC

Study Title: Adhesive Versus Endotracheal Tube Fastener

Institution: Vanderbilt University Medical Center

Version Date: 3/21/2018

dislodgement of the endotracheal tube (i.e. accidental extubation) or needing to reposition the endotracheal tube more than 1 cm (i.e. need to pull ETT back 2+ cm or move it down 2+ cm).

The following study endpoints will be collected if they occur anytime between randomization and the earlier of death, hospital discharge, tracheostomy placement, or 48 hours after extubation: lip ulcers, facial skin tears, tube dislodgement, and ventilator associated pneumonia.

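### For ICU intubations, allocation and the endpoint window precede tube placement, and no lip or face check is scheduled at securement, so intubation injuries can count as endpoint events and dilute the relative effect

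*Combined protocol and SAP*

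**What the plan says.** **Enrolment and allocation.** Section 6.3 states: "All patients will be enrolled at the time the clinical team decides that intubation is required". Section 6.5 places the opening of the envelope at the same point: "Once it has been determined by the treating team that intubation is required", after which "the operator will open the envelope and follow the assignment of either adhesive tape or endotracheal tube fastener". For patients who arrive already intubated, 6.3 instead places randomization at the time the tube is being secured, within 12 hours of intubation.

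**Endpoint window.** The primary endpoint in 1.0 (a composite of lip ulcer, tube dislodgement or facial skin tear) runs "from the time of randomization to the earlier of death or 48 hours after extubation". Section 8.0 uses the same start: "The following study endpoints will be collected if they occur anytime between randomization and the earlier of death, hospital discharge, tracheostomy placement". Its one further closing point is again the 48-hour mark following extubation.

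**Skin and mucosa status.** The exclusion for oral mucosa or facial skin breakdown (1.0 and 5.2) refers to the state before enrolment. At securement, 8.0 lists only "Depth of tube as measured at lip line and position in mouth". Oral mucosa and facial skin assessments appear under in-hospital outcomes with no time point. No section requires a lesion to be new since securement.

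**Baseline list.** Section 8.0 includes "whether the face was soiled during the intubation" among the baseline items.

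**The concern.** For an ICU intubation the order is: decision, envelope, laryngoscopy and tube placement, device. Follow-up for lip ulcers and skin tears is already running during the third step, when neither device can have caused anything. The exclusion was applied before that step and nothing is scheduled after it, so the plan has no point at which an intubation injury would be noted and set aside. Such injuries enter both arms and weaken the relative contrast between tape and fastener.

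For patients who arrive intubated, any intubation injury precedes enrolment and can be caught by the exclusion. The same endpoint therefore covers different exposures in the two entry routes.

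Early opening also lets a patient be randomized and then never intubated. Such a patient has no ventilator days, so the rate per 1,000 ventilator days in 12.4 is undefined, while 12.2 promises an intention-to-treat analysis.

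**Working it through.** **Plan's own figures (12.1).** The combined rate is 20 + 1.1 = 21.1 per 1,000 ventilator days. With difference 5, SD 15, 80% power and two-sided alpha 0.05, n per arm = 2 × [15 × (1.960 + 0.842) / 5]² = 141.3, rounded up to 142. This reproduces the stated figure, and the timing point does not alter it.

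**Inputs for the illustration.** From the plan: 500 patients randomized 1:1, so 250 per arm; 1.1 lip ulcers and 21.1 combined events per 1,000 ventilator days; a target difference of 5, so 16.1 in the better arm. Assumed, because the documents give no figure: D = 5 to 10 ventilator days per patient, and q = 0.5% to 3% of patients with an intubation lesion that qualifies as a lip ulcer or facial skin tear. Applying q to all 250 gives an upper bound, since patients who arrive intubated are unaffected and their share is not stated.

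**Expected counts per arm.**

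| Quantity | D = 5 (1,250 days) | D = 10 (2,500 days) |
|---|---|---|
| Lip ulcers at 1.1 per 1,000 | 1.4 | 2.8 |
| Combined events at 21.1 per 1,000 | 26.4 | 52.8 |

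Added lesions: 0.005 × 250 = 1.25 to 0.03 × 250 = 7.5.

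- Relative to lip ulcers: 1.25 / 2.75 = 0.45 to 7.5 / 1.375 = 5.5 times.
- Relative to combined events: 1.25 / 52.75 = 2% to 7.5 / 26.375 = 28%.

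The 21.1 covers dislodgement and lip ulcer only. If skin tears or ventilator associated pneumonia are added to the denominator, the share falls.

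**Effect on the comparison.** Intubation lesions add 1000q/D per 1,000 ventilator days to each arm.

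- No lesions: 16.1 / 21.1 = 0.763.
- q = 0.5%, D = 10: adds 0.5, giving 16.6 / 21.6 = 0.769.
- q = 3%, D = 5: adds 6.0, giving 22.1 / 27.1 = 0.815.

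The absolute rate difference stays at 5. For a yes/no composite with device-era risks p1 and p2, and lesions independent of later events, the risk difference becomes (1 − q)(p1 − p2), a shrinkage of at most 3% here.

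**Which endpoints are exposed.** Under 1.0, both lip ulcers and skin tears carry the extra events, in the composite and as separate secondary endpoints. The primary endpoint in 12.4 omits skin tears, so there the route is mainly through lip ulcers.

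**The case against.** **The sequence could be later than it looks.** Section 6.5 can be read as giving the earliest moment for opening the envelope. Section 7.1.1 goes straight from the open envelope to securement, and inclusion criterion 3 in 1.0 speaks of patients already intubated for under 12 hours at enrolment. That ambiguity is real, but 6.3 is explicit that enrolment is at the decision to intubate, and nothing overrides it.

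**The status at securement may be recoverable.** Skin and mucosa assessments come from usual care, and 4.0 mentions data collection at the time of intubation. Routine charting may therefore show onset. The plan neither requires nor uses it.

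**Stronger readings that a reader might infer, and why they fail:**

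- *The result is biased towards one arm.* Injuries unrelated to the device fall equally on randomized arms in expectation. A differential effect would need knowledge of the arm to change the intubation or the recording of lesions, and the documents do not show that.
- *Intubation lesions would swamp the endpoint.* At the low end they are fewer than half the expected lip ulcers. Lip ulcers themselves are 1.1 of the 21.1 combined rate.
- *The window never closes for a patient who is never intubated.* Section 8.0 also closes it at death or hospital discharge. Only the 12.4 rate is undefined; under the 1.0 composite such a patient can be counted as having no event.
- *The soiled-face item distorts the analysis.* It is not in the 12.3 list, analyses are unadjusted, and no stated analysis uses it. The issue is its label.

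**Conclusion.** The point holds for patients intubated in the ICU. As written, a lip ulcer or facial skin tear caused by intubation is an endpoint event, and time zero differs between entry routes. The consequence is dilution: under the stated assumptions the target rate ratio of 0.763 moves to between 0.769 and 0.815, with the absolute rate difference unchanged. The effect on the combined endpoint is small to moderate. It matters most for the lip-ulcer and skin-tear endpoints, where device-related events may be few. The lesion risk, the ventilator days and the share of patients intubated in the ICU are not in the documents, so the size is illustrative and the lesion count an upper bound for the assumed risks. The number of patients randomized but never intubated cannot be estimated from the documents. The change is worth making because it is cheap and the status at securement may not be recoverable afterwards.

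**What to change.** 1. **6.3 and 6.5:** for ICU intubations, open the envelope after oral tube placement is confirmed and immediately before securement, as 6.3 already does for patients who arrive intubated. Reconcile this with inclusion criterion 3 in 1.0. This gives both routes the same time zero and avoids randomizing patients who are never intubated.
2. **8.0, Periprocedural:** add lip, oral mucosa and facial skin status, recorded before the envelope is opened. Apply the breakdown exclusion at that check, and count only lesions not present then.
3. **If the envelope must be opened earlier:** record the same check before the device is applied and count only new lesions. State that staff who may know the arm make this check; calling a lesion pre-existing could then differ by arm, which is why the first option is better. State how patients who are never intubated enter the 12.4 analysis, and relabel the soiled-face item as periprocedural.

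The cost is wording in three sections and a short addition to the bedside sheet, with no change to the sample size. Both devices must be at hand at intubation, and a few patients with intubation injury will not be enrolled.

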## **7.0 Study Procedures**

### **7.1 Study Interventions**

#### **7.1.1 Endotracheal Tube Securement**

Once the envelope is opened and group assignment known, the clinical team will either secure the endotracheal tube with either adhesive tape or the endotracheal tube fastener. In patients randomized to adhesive tape, the respiratory therapist will secure the endotracheal tube with adhesive tape as demonstrated in figure 1. In patients randomized to endotracheal tube fastener, the respiratory therapist will secure the endotracheal tube with the Hollister endotracheal tube fastener per the manufacturer's instructions (demonstrated in figure 2).

#### **7.1.2 Endotracheal Tube Repositioning**

Prior studies investigating endotracheal tube securement techniques require that the endotracheal tube is repositioned and retaped every 24 hours (1,2). However, due to the pragmatic design and intent of this protocol, the endotracheal tube will not routinely be repositioned specifically as part of the study protocol. The tube will be repositioned as needed according to ICU policy or protocols or at the discretion of the provider, bedside nurse, or respiratory therapist.

